2.2 Secondary Objectives

1. To correlate mutations in the mTOR pathway with therapeutic response to everolimus.
2. To investigate the genetic changes associated with disease progression following treatment with everolimus.

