14.0 STATISTICAL CONSIDERATIONS

14.1 Study Design

This is an open label, single-arm phase II trial focusing on the response rate of the therapeutic agent. Since this is a study in patients with specifically targeted mutations, a rather big treatment effect size is expected. Based on historical data, we assume a null hypothesis of an overall response rate of <1% in this setting.⁹ We hypothesize that an overall response rate of 30% or higher warrants further investigation. A total of N=12 patients will be enrolled for this study, based on the exact single-stage design with 85% power at a 1-sided 0.05 significance level (using *ph2single* function from library *clinfun* in the R package). If 2 or more responders are observed out of these 12 patients, we would conclude that preliminary evidence for efficacy exists and that further investigation of the treatment is warranted.

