14.2 Data Analysis

The primary endpoint will be to describe the response rate using RECIST 1.1. Response rate will be defined as complete response (disappearance of all target lesion) plus partial response (a least a 30% decrease in the sum of diameters of target lesions). Secondary endpoint will be to further evaluate molecular markers of response or resistance using exome sequencing and transcriptome sequencing when feasible.

Demographic and clinical characteristics of the sample, as well as response, and toxicity by grade will be summarized using descriptive statistics. The overall response rate and its 90% confidence interval will be estimated. If possible, permutation tests will also be performed to compare the differences of secondary endpoints between responders and non-responders. The distribution associated with no difference (the null distribution) can be identified using the data in hand. If there is no difference between the values seen in responders and those in non-responders, then, for this purpose, it does not matter whether a given patient is labeled as a responder or a nonresponder. So we can randomly shuffle the response labels and calculate the test statistic from the shuffled data. If this procedure is repeated 10,000 times, the resulting 10,000 test statistics provide an accurate representation of the null distribution. The observed test statistic, based on patients assigned to the correct response group, is then compared to the null distribution. If the observed test statistic is unusually large or small, so very few values from the null distribution are larger or smaller than the observed test statistic, then the observed difference between responders and non-responders is unlikely if the null hypothesis were correct. In that case, we can reject the null hypothesis of no difference and conclude that there is a true difference between responders and non-responders. Then the null distribution

of the test statistics will be generated by simulating 10,000 datasets where the status of response was randomly shuffled. In order to quantify the extent to which the observed test statistic is “unusual,” a permutation test generates a p-value, which is equal to the proportion of test statistics from the label-shuffled samples that exceed the observed test statistics.

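### Section 14.2 applies a single-test rule (reject, then claim a true difference) to exome and transcriptome markers in 12 patients, with no marker family, significance level, multiplicity control or exploratory label

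*Combined protocol and SAP*

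**What the plan says.** Section 14.1 fixes the size: "A total of N=12 patients will be enrolled for this study". It sets the target for the primary endpoint: "We hypothesize that an overall response rate of 30% or higher warrants further investigation". The only error rate in the plan belongs to that endpoint, an "exact single-stage design with 85% power at a 1-sided 0.05 significance level".

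Section 2.2 lists as the first secondary objective: "To correlate mutations in the mTOR pathway with therapeutic response to everolimus". Section 14.2 is wider. Its secondary endpoint is to evaluate "molecular markers of response or resistance using exome sequencing and transcriptome sequencing when feasible". Permutation tests with 10,000 shuffles are to compare responders with non-responders, if possible. When the observed statistic is unusual against the shuffles, the instruction is: "In that case, we can reject the null hypothesis of no difference and conclude that there is a true difference between responders and non-responders". The p-value is defined as the share of shuffled statistics greater than the observed one.

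For these tests the plan gives no list or number of markers, no numerical threshold, no multiplicity or false-discovery control, no statement that the results are exploratory, and no validation step. Sidedness is also unclear: the explanation speaks of both unusually large and unusually small statistics, while the p-value counts one direction only.

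**The concern.** The rule is sound for one marker chosen before the data are seen. Exome and transcriptome data can supply thousands. Applied marker by marker, the same rule turns the expected yield of chance into statements of true difference. This is more than a missing detail, because the plan states the conclusion to be drawn and supplies nothing to limit how often it is drawn wrongly. The answer to the marker endpoint, and to the first secondary objective if it is analysed this way, could then be presented as established when the data cannot carry that claim.

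The p-value definition adds a second fault. When the observed labelling is the most extreme one, no shuffle lies above it and p is 0. No later correction of p-values removes a zero.

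**Working it through.** **The plan's own figure.** Section 14.1 takes a null response rate below 1% (0.01 used here), a target of 30%, and success at 2 or more responders of 12.
- Level: 1 − 0.99^12 − 12 × 0.01 × 0.99^11 = 1 − 0.8864 − 0.1074 = 0.0062.
- Power: 1 − 0.7^12 − 12 × 0.3 × 0.7^11 = 1 − 0.0138 − 0.0712 = 0.915.

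The design meets its stated limits. The stated 85% power would need only 10 patients (rule of 2 or more, level 0.0043, power 85.1%). That gap is conservative and does not bear on this point.

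**Inputs for the permutation tests.** From the documents: 12 patients, and 12 × 0.30 = 3.6 responders expected at the target rate. Assumed, because the documents give neither: a threshold of 0.05 for each test, and 100 to 20,000 markers.

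**Labellings and smallest p.** With k responders there are L = C(12, k) distinct labellings, and a valid one-sided p cannot be below 1/L. For a continuous null marker, the chance of p ≤ 0.05 is floor(0.05 L)/L when the observed labelling is counted. With the strict definition in Section 14.2 it is (floor(0.05 L) + 1)/L.

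| Responders | L | Smallest valid p | Null share, valid p | Null share, as written | Null markers with p = 0, of 20,000 |
|---|---|---|---|---|---|
| 2 | 66 | 0.0152 | 3/66 = 4.5% | 4/66 = 6.1% | 20,000/66 = 303 |
| 3 | 220 | 0.0045 | 11/220 = 5.0% | 12/220 = 5.5% | 20,000/220 = 91 |
| 4 | 495 | 0.0020 | 24/495 = 4.8% | 25/495 = 5.1% | 20,000/495 = 40 |

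With one responder, L = 12. A valid p cannot be below 0.083, yet the written definition gives p = 0 for one null marker in 12.

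**Expected false declarations with valid p-values.**
- 100 markers: about 5.
- 500 markers: 23 to 25.
- 20,000 markers: 20,000 × 3/66 = 909, 20,000 × 24/495 = 970 and 20,000 × 11/220 = 1,000 with 2, 4 and 3 responders.
- Five independent markers at 0.05: 5 × 0.05 = 0.25 expected, and a chance of 1 − 0.95^5 = 22.6% of at least one.

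**Share of declared markers that are false.** With a fraction f of markers real, the share is 0.05(1 − f) / [0.05(1 − f) + power × f]. Power is taken from 80% down to 20%. Simulated two-sided power with 2, 3 and 4 responders was 20%, 28% and 32% for a 1-SD difference, and 61%, 77% and 82% for 2 SD.

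| Real markers | False share (power 80% to 20%) |
|---|---|
| 0.1% | 98% to 99.6% |
| 1% | 86% to 96% |
| 5% | 54% to 83% |
| 10% | 36% to 69% |
| 20% | 20% to 50% |

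**Sparse mutation calls.** For a present/absent marker with one carrier among 12, p with ties counted is at least k/12: 0.167, 0.25 or 0.33 with 2, 3 or 4 responders. With two carriers and four responders it is at least C(4,2)/C(12,2) = 6/66 = 0.091. Neither can be declared at 0.05, so the rates above apply to continuous data such as expression and not to sparse mutations.

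**The case against.** The strongest reply is that the sentence sits in a general explanation of how a permutation test works. The tests are to be done only if possible and the sequencing only when feasible. No marker count, threshold or statistic is given, so nothing says that every feature will be tested separately. Much of this stands, and it limits what can be claimed.

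- A reader might infer that the reported markers would be mostly or wholly chance. The documents do not support that. It needs a marker count, a threshold and a share of real markers that they do not give. A false majority is not assured if 10% or more of markers are real, and *wholly* would require that no marker is real or detectable.
- A reader might infer that a later correction could not help. It could. If a Bonferroni correction with valid p-values rejected nothing, the false list would be prevented at the cost of power. False-discovery control is not arithmetically barred either: with 4 responders it needs i × 0.05/20,000 ≥ 1/495, so 809 of 20,000 features at the smallest p would pass at 5%.
- A reader might infer that the marker list decides which biomarkers go forward. No section says so. The only go-forward rule is the responder count in Section 14.1, which is unaffected.
- Section 2.2 speaks of the mTOR pathway and names no genes, so it does not itself define a family.

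What does not stand is the defence that the text is only explanatory. It is the only inference rule the plan gives for this endpoint. The conditional wording governs whether the tests are run, not what is concluded when they are.

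**Conclusion.** The point holds in a limited form. Section 14.2 carries a single-test conclusion over to genome-scale markers with nothing to control false claims. The expected 4.5% to 5.0% of null markers declared rests on continuous markers, separate tests and an assumed 0.05; the totals rest on assumed marker counts. Under those conditions most declared markers would be false unless real ones are common. With a short list the problem is smaller but still material. The p-value fault needs no assumption about the number of markers, since the strict definition allows p = 0 even for one test. The change should be made, but the primary endpoint and its decision rule are not affected.

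**What to change.** In Section 14.2:

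1. Replace the claim of a true difference with wording that calls marker results hypothesis-generating.
2. Pre-specify a short family for the first secondary objective. The five genes listed in Sections 2.1 and 3.1 (TSC1, TSC2, NF1, NF2, STK11) are one workable choice. By eligibility every patient carries a mutation in at least one of them, so the comparison is between genes.
3. Test that family with the single-step maximum statistic (max-T) from the same shuffles, at a stated significance level and sidedness.
4. Count ties and the observed labelling in p: use greater than or equal, or (b + 1)/(B + 1), where B is the number of shuffles and b the number at or above the observed statistic.
5. Report all other exome and transcriptome features as a ranked descriptive list without significance claims.

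This needs no new patients, samples or assays, only a wording change and a small addition to code already planned. The price is fewer markers called significant. With one responder nothing can reach 0.05, and with 2 to 4 responders a gene carried by one patient cannot either.

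### The permutation p-value in Section 14.2 leaves out ties, so yes/no mutation markers in 12 patients get p-values that are too small, sometimes exactly zero

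*Combined protocol and SAP*

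**What the plan says.** Section 14.2 (Data Analysis) introduces the tests conditionally: "If possible, permutation tests will also be performed to compare the differences of secondary endpoints between responders and non-responders". The response labels are shuffled 10,000 times to build the null distribution. The rationale is worded in both directions: "If the observed test statistic is unusually large or small, so very few values from the null distribution are larger or smaller" than the observed value. In that event, the section says, "we can reject the null hypothesis of no difference and conclude that there is a true difference between responders and non-responders". The paragraph closes with the operative definition, "a p-value, which is equal to the proportion of test statistics from the label-shuffled samples that exceed the observed test statistics".

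Both sentences use strict comparisons. The section does not say what happens to ties, what the test statistic is, whether the test is one- or two-sided, or what threshold applies.

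The first objective in Section 2.2 is "To correlate mutations in the mTOR pathway with therapeutic response to everolimus". Section 14.2 names exome and transcriptome sequencing as the source of the markers. Section 14.1 sets the sample at 12 patients and calls the result promising if 2 or more respond.

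**The concern.** A permutation p-value is the probability, over relabellings, of a result at least as extreme as the one seen. Counting only results strictly beyond it gives the smaller quantity P(T* > T). The difference is the probability of the tied results.

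With 12 patients and a yes/no marker the statistic takes only a handful of values, so that probability can be large. The largest attainable value of the statistic always receives p = 0, however often chance produces it. This is so whether the statistic is signed or absolute.

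The undefined statistic is a second problem. The formula counts upwards only. If the statistic is the signed difference, responders minus non-responders, a marker concentrated in non-responders gets a p-value near 1. If it is the absolute difference, it does not.

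What is at stake is the marker conclusions: chance patterns could be reported as real differences, in a section that permits exactly that wording.

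**Working it through.** **Inputs.** From the plan: 12 patients and the 2-responder success rule (14.1); 10,000 shuffles and the strict p-value rule (14.2). Assumed, because the plan gives none: a binary marker carried by m of the 12 patients; r responders; T = carrier proportion in responders minus that in non-responders, signed or absolute; a 0.05 threshold.

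**The plan's own figures.** No permutation p-value is stated, so there is none to reproduce. The 2-of-12 rule does meet its stated targets: at a 1% response rate the chance of 2 or more responders is 0.0062, and at 30% it is 0.915.

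**Formula.** With k carriers among r responders, P(k) = C(m,k)·C(12−m, r−k)/C(12,r) under the null. The written rule is P(T* > T); the valid rule is P(T* ≥ T).

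**Example 1: r = 2, m = 6, both responders carriers.**
- There are C(12,2) = 66 labellings. k = 2, 1, 0 give T = 0.6, 0, −0.6, with 15, 36 and 15 labellings.
- Written rule: nothing lies beyond 0.6, so p = 0, signed or absolute.
- Valid: 15/66 = 0.227 signed; (15+15)/66 = 0.455 absolute.
- A literal run of 10,000 shuffles gave 0.000 under the written rule for both statistics. With (b+1)/10,001 it gave 0.228 and 0.455.

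**Example 2: r = 3, m = 6, all responders carriers.** Written p = 0. Valid: 20/220 = 0.091 one-sided, 40/220 = 0.182 two-sided.

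**Example 3: r = 2, m = 3, absolute statistic.** k = 0 gives |0 − 3/10| = 0.3; k = 1 gives |1/2 − 2/10| = 0.3; k = 2 gives |1 − 1/10| = 0.9. Only k = 2, with 3/66 = 0.045, lies beyond 0.3. So k = 0 and k = 1 both get p = 0.045 and k = 2 gets 0: every possible dataset is significant at 0.05.

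**Example 4, sidedness: r = 2, m = 9, no responder a carrier.** T = 0 − 9/10 = −0.9. Signed, the written p is 63/66 = 0.955. Absolute, it is 0. The valid two-sided value is 3/66 = 0.045.

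**Rejection of a true null at 0.05, over m = 1 to 11:**

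| Responders | Labellings | Written rule, signed | Written rule, absolute | Ties counted, maximum | Untied continuous marker, written rule |
|---|---|---|---|---|---|
| 2 | 66 | 9.1% to 83.3% | 9.1% to 100% | 4.5% | 4/66 = 6.1% |
| 3 | 220 | 9.1% to 75.0% | 12.7% to 100% | 4.5% | 12/220 = 5.5% |
| 4 | 495 | 6.7% to 66.7% | 6.1% to 49.1% | 3.0% | 25/495 = 5.1% |

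The continuous column follows because j labellings lie strictly beyond the observed one with j = 0, 1, 2, …, and the rule rejects when j/C(12,r) ≤ 0.05. For 66 labellings that is j = 0 to 3, or four outcomes.

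**The case against.** The best counter-argument is that the paragraph explains permutation testing in general terms and that its strict wording is loose language for *at least as large as*. A competent programmer might count ties anyway. That is possible, but nothing in the documents says so, and the sentence is a definition that could be coded literally.

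Several limiting points stand:
- The 0.227 and 0.455 come from one illustrative case, not a general range. Over 1 to 6 responders and 1 to 11 carriers, the valid one-sided value where the written rule gives 0 runs from about 0.001 to 0.92. Some cases are harmless: with 2 carriers who are the 2 responders, the valid value is 1/66 = 0.015.
- At a 30% response rate, 3 or 4 responders (24% and 23%) are each likelier than 2 (17%). With 4 responders, all among 6 carriers, the valid values are 0.030 and 0.061, so the gap is smaller.
- Omitting the observed labelling by itself changes p by at most about 0.0001 with 10,000 shuffles. The ties do the damage.
- Binary coding is inferred from the mutation objective. Expression data could be continuous, and there the excess is about 1 percentage point or less.
- The 100% rates are corner cases of the absolute statistic.
- The two-directional rationale in Section 14.2 partly answers the sidedness point, since it would flag Example 4 as unusually small. The formula would still report 0.955.

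These points limit the weight of the problem. They do not make the stated formula correct.

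**Conclusion.** The concern holds. As written, the formula is anti-conservative, and for yes/no markers in 12 patients the error is large: the false-positive rate exceeds 5% at every carrier count from 1 to 11 with 2, 3 or 4 responders, for either form of the statistic. This rests on binary coding, a difference-in-proportions statistic, a 0.05 threshold and literal implementation. The missing statistic and sidedness can by themselves reverse a conclusion, as 0.955 against 0 shows.

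The reach is narrow. These are secondary tests, done only if feasible, and they feed no decision rule. The 2-of-12 criterion and the response-rate confidence interval are untouched. It should be corrected before any marker is analysed, so that the choice cannot depend on the results.

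**What to change.** In Section 14.2, state a two-sided statistic: for example, the absolute difference between responders and non-responders, in proportions for mutation markers and in means or mean ranks for continuous ones. Replace the p-value sentence with p = (b+1)/(10,000+1), where b is the number of shuffled statistics at least as large as the observed one. Alternatively, enumerate all C(12,r) labellings (66, 220 or 495 for 2, 3 or 4 responders) and report the share at least as extreme, the observed labelling included. Bring the rationale sentence into line with the same comparison.

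This takes a sentence of text and a line of code, with no new data. The price is larger p-values: with 2 responders, a two-sided test of a binary marker can then reach 0.05 only if 2, 3, 9 or 10 of the 12 patients carry it. That limit reflects the sample size and is worth stating in the plan.

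### Section 14.2 rejects on both tails but computes the permutation p-value from the upper tail only, and it does not define the test statistic

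*Combined protocol and SAP*

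**What the plan says.** Section 14.2 of the combined protocol and SAP sets the secondary analysis: "Secondary endpoint will be to further evaluate molecular markers of response or resistance", by sequencing where feasible. If possible, "permutation tests will also be performed to compare the differences of secondary endpoints between responders and non-responders".

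The null distribution comes from "simulating 10,000 datasets where the status of response was randomly shuffled". The rejection rule is then put in two-tailed terms: "If the observed test statistic is unusually large or small, so very few values from the null distribution are larger or smaller" than the observed one. In that case the analyst is to "reject the null hypothesis of no difference and conclude that there is a true difference between responders and non-responders". No direction is named.

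The paragraph closes by defining the p-value that measures how unusual the result is. It is "equal to the proportion of test statistics from the label-shuffled samples that exceed the observed test statistics".

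The section does not say what the statistic is, whether it is signed or absolute, or in which order the groups are subtracted. It gives no significance level or sidedness for these tests. The one-sided 0.05 in Section 14.1 belongs to the response-rate design.

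**The concern.** The rejection rule and the p-value are meant to describe the same test, but they do not. A share of shuffled statistics lying above the observed one cannot show that the observed one is unusually small. For a signed statistic it approaches 1 in exactly that case.

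Both directions matter here. The endpoint covers markers of response and markers of resistance, and Section 1.4 gives resistance markers as part of the rationale. A marker enriched in non-responders is lower in responders. A p-value that looks at one tail can therefore pass over half of what the analysis is meant to find. If the tail is settled only after the marker data are seen, the choice depends on the data.

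**Working it through.** The plan gives no figure for the permutation analysis, so there is none to reproduce. The check applies the p-value as written.

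**Inputs.** N = 12 patients (Section 14.1). For k responders I take 2, the success threshold in Section 14.1, and then 3 and 4, which bracket 30% of 12 = 3.6. The statistic T is assumed to be the responder mean minus the non-responder mean. The marker values are assumed distinct, with the k lowest all in responders.

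**Formulas.** There are L = C(12, k) equally likely labellings. The observed labelling has the smallest T of all, so the other L − 1 exceed it:

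- written p = (L − 1)/L
- smaller tail, counting the observed labelling = 1/L, and doubled = 2/L

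| k | L | Written p | Twice smaller tail |
|---|---|---|---|
| 2 | 66 | 65/66 = 0.985 | 2/66 = 0.030 |
| 3 | 220 | 219/220 = 0.995 | 2/220 = 0.009 |
| 4 | 495 | 494/495 = 0.998 | 2/495 = 0.004 |

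Random shuffling, 10,000 times as the plan specifies, gave a written p of 0.984 for k = 2 and 0.998 for k = 4.

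**Imperfect separation.** I simulated 4,000 normal datasets per setting, with an assumed shift of 2 SD and an assumed 0.05 level. For a marker lower in responders, the written p-value rejected in 0% of datasets at k = 2, 3, 4 and 6. Counting shuffles with |T| at least as large as observed rejected in 61%, 77%, 83% and 88%.

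**Order of subtraction.** With non-responder minus responder, T changes sign and the same figures apply to markers that are higher in responders.

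**Unsigned statistic.** If T is an absolute difference, its upper tail already covers both directions, apart from how ties are counted. An unusually small value then means the groups are nearly identical, so the clause about small values would call close agreement a true difference.

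**Which two-sided version.** Doubling the smaller tail and using |T| agree for equally spaced values, but not for skewed ones. I took 12 assumed lognormal scores, exp(σz), with z the normal quantile at (i − 0.5)/12, and put the lowest values in responders:

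| k | |T| version, σ = 1 | |T| version, σ = 0.5 | Twice smaller tail, either σ |
|---|---|---|---|
| 2 | 12/66 = 0.182 | 0.076 | 0.030 |
| 3 | 21/220 = 0.095 | 0.032 | 0.009 |
| 4 | 22/495 = 0.044 | 0.012 | 0.004 |

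The few responders share out the long upper tail. Many labellings that place a high value among the responders therefore produce a large positive T, and these count against a low-in-responder marker when |T| is used.

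**The case against.** The strongest reply is that the harm is conditional. The statistic is undefined. With an absolute, squared or chi-square-type statistic the upper-tail share is already two-sided, and no marker is missed. This stands. The loss of one direction can be claimed only for a signed statistic, and the loss of low-in-responder markers only for responder minus non-responder. A reader might infer that the plan will certainly miss resistance markers. The documents do not support that, because they fix neither condition. The signed reading does fit the paragraph better, since rejecting on small values has no sensible meaning otherwise.

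A second reply is that an analyst following the verbal rule would notice a p-value near 1 and act on it. That is possible, so the text is ambiguous rather than committed to a test that is blind in one tail. The reported p-value would still contradict the decision. A reader might also infer that acting on both tails at 5% gives a 10% error rate. The plan states no level for these tests, so that figure is not available from the documents.

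Third, little depends on the result. The tests are secondary and conditional on feasibility, in 12 patients. No stated decision uses a marker p-value. Resistance is also studied through the genetic changes at progression (Section 2.2) and the progression biopsies (Section 9.2). This stands and sets the weight of the point.

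**Conclusion.** The point holds as an internal inconsistency: a two-tailed rule is paired with an upper-tail p-value, and the missing definition of the statistic leaves it unresolved. Under a signed statistic, one direction of difference cannot be detected by the written p-value. A perfectly separated marker in that direction gets 0.985 to 0.998 with 2 to 4 responders, against 0.030 to 0.004 for twice the smaller tail. Those figures need distinct marker values but no particular distribution. The rejection rates rest on the assumed normal data, 2 SD shift and 0.05 level. Under an unsigned statistic the p-value has the right direction and the verbal rule is wrong.

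Severity is minor. The primary rule of at least 2 responders in 12 is untouched.

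**What to change.** Amend Section 14.2 before any marker data are analysed:

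1. Define the statistic, for example the responder minus non-responder mean difference.
2. For each tail compute (b + 1)/(10,000 + 1), where b is the number of shuffled statistics at least as extreme as the observed one in that direction, ties included. The p-value is twice the smaller of the two, capped at 1.
3. Reword the sentence on large or small statistics to match.

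Doubling the smaller tail is preferable to the absolute mean difference because skewed markers and few responders are likely here. A rank-based statistic would also avoid the skewness problem.

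The cost is a few sentences and no new data. In the direction the current formula detects, p-values become about twice as large, and a written p of 0 (the most extreme upper-tail labelling, since only strictly larger values are counted) becomes a small positive value. Some power is lost in that direction. In the simulation above, for a marker 2 SD higher in responders, rejection fell from 78% to 60% with 2 responders and from 91% to 82% with 4 (|T| version). With 2 responders and the doubled tail, only perfect separation falls below 0.05: 2/66 = 0.030, and the next value is 4/66 = 0.061.
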